## 12.2 Data analysis and reporting

The data will be collected from each center in the eCRF data base via Oracle Clinical. A specific account number will be given to each center to access the system from any internet-enabled computer. Access to Internet is required for the sites to enter data into the system. User Identification codes will be created to identify data input from each center. The clinical data will be entered by the study staff and transmitted to the central database in an anonymous format so that the study sponsor will not be able to identify the patient, in accordance with the European Data Privacy Directive. Electronic automatic and manual queries will be generated for missing, incorrect or doubtful data and sent directly to the study center via Oracle Clinical. All the detailed data analyses are described in the Statistical Analysis Plan. Any deviations from this section and/or the Statistical Analysis Plan will be described and justified in the Final Clinical Study Report, as appropriate.

## 12.3 Analysis of clinical data

Patient demographics and baseline characteristics will be presented using appropriate summary statistics. This includes mean and standard deviation, minimum, maximum and median with the interquartile range [IQR] for continuous variables and counts and percentages for categorical variables. Summary statistics will be reported with maximum 2 decimals, as appropriate. The SAS software (SAS Institute Inc., Cary, NC, USA) will be used to perform statistical analyses. Statistical tests will be based on a two-sided significance level of 0.05. Graphical representations will be used as deemed appropriate. No adjustments for multiple comparisons or multiple look at data will be performed. Outliers and influential observations will be identified via graphical plots and according to study team decision the analysis could be repeated excluding potential outliers. In case of missing data, no imputation method will be implemented for analysis.

The Full Analysis Set (FAS) will be used for primary final analysis. Any patient who does not satisfying the inclusion/exclusion criteria will be eliminate from the FAS population. Details of endpoints analyses and additional analysis will be described in the Statistical Analysis Plan. The analyses of primary objective on the proportion of patient with at least one RC markers will be reported together with their 95% confidence intervals and separately for each arm and phase of the study (see primary endpoint definition). When comparison of clinical primary outcomes is conducted the propensity score methods could be used to control for biases and confounding which may be due to the nature of this study. The

difference between the two groups within phase and between phases within groups will be analyzed by means of unpaired t-test or Mann-Whitney test according to the normal or non-normal distribution. For one secondary outcome the logistic regression model will be used to check potential predictors. Bivariate odds ratios (ORs) and 95% confidence intervals (95% CIs) will be estimated for each predictor. A multivariate logistic regression model will be performed according to univariate model's results. Other secondary outcomes will be performed using sensitivity and specificity analysis.

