The analysis of primary objective will be based on the proportion of patients with at least one RC marker; it will be reported together with their 95% confidence intervals and separately for each arm and phase of the study. When comparison of clinical primary outcomes is conducted the propensity score methods could be used to control for biases and confounding which may occur due to the nature of this study. For all secondary outcomes the logistic regression model will be used to check potential predictors.

Bivariate odds ratios (ORs) and 95% confidence intervals (95% CIs) will be estimated for each predictor. A multivariate logistic regression model will be performed according to univariate model's results. Other secondary outcomes will be performed using sensitivity and specificity analysis.

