## 12. Statistical Design and Methods

### 12.1 Sample size justification

The sample size calculation is based on primary endpoint and it was estimated using data from previous studies with a precision-based calculation. Recent data on post-surgical patient have shown a proportion of patient with the RC markers for the SpO2 ≤ 85% for ≥ 3 minutes at 13% and for RR ≤ 8 or ≥ 22 bpm

for  $\geq 3$  minutes at 1.4% in patients undergoing opioid therapy. Using this information, a minimum proportion of 10% of patients with RC markers with a sample size of 260 patients will be able to obtain a 95% confidence level with a precision of 5% (ranging from 5% to 10%) and a power of at least 0.80 defined as the probability of achieving the desired precision. Considering a 10% withdrawal or potential dropouts and a potential attrition rate to monitoring compliance of 5% a total of approximately 210 patients will be enrolled. This cohort will be used prospectively for the blinded and not blinded phase with a ratio 1:2 respectively to minimize not blinded monitored patients. The blinded phase will enroll 70 patients randomly allocated 1:1 in the Capnostream 20p and PM1000N-RR arm while the not blinded phase will enroll 140 patients with same randomized schedule.

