## 6. Determination of Sample Size

The sample size calculation is based on primary endpoint and it was estimated using data from previous studies with a precision-based calculation. Recent data on post-surgical patient have shown a proportion of patient with the RC markers for the  $\text{SpO}_2 \leq 85\%$  for  $\geq 3$  minutes at 13% and for  $\text{RR} \leq 8$  or  $\geq 22$  bpm for  $\geq 3$  minutes at 1.4% in patients undergoing opioid therapy. Using this information, a minimum proportion of 10% of patients with RC markers with a sample size of 182 subjects will be able to obtain a 95% confidence level with a precision of 5% (ranging from 5% to 10%) and a power of at least 0.80 defined as the probability of achieving the desired precision. Considering a 10% withdrawal or potential dropouts and a potential attrition rate to monitoring compliance of 5% a total of approximately 210 subjects will be enrolled. This cohort will be used prospectively for the blinded and not blinded phase with a ratio 1:2 respectively to minimize not blinded monitored subjects. The blinded phase will enroll

70 subjects randomly allocated 1:1 in the Capnostream 20p and PM1000N arms while the not blinded phase will enroll 140 subjects with same randomized schedule.

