### 7.9.2. Secondary Endpoints

The secondary endpoints are:

1. To compare phases in terms of Primary endpoint incidence;
2. To compare phases in terms of respiratory and SAE incidence, number of ICU transfers and related length of stay, Code blues and RRT responses.
3. To evaluate the rate of clinical early interventions performed by nurse staff to prevent a potential AE, introducing continuous monitoring devices connected to a remote monitoring platform;
4. To evaluate the nurses’ satisfaction related to the monitoring system introducing continuous monitoring devices connected to a remote monitoring platform;
5. To establish the Predictive values of  $\text{EtCO}_2$ , RR,  $\text{SpO}_2$ , plethysmography-derived RR, IPI and EWS in respect to respiratory and other SAE.

In order to evaluate secondary **endpoints #1 and #2**, the incidence of events will be reported together with the comparison between phases, by means of the Chi-square test or Fisher exact test for extreme

proportions, as appropriate. If the monitoring/study exposure results different between phases, also the rates of events will be reported, together with the 95% Poisson Confidence Intervals. The Poisson regression model will be used to calculate the Incidence Rate ratio (IRR), with the d-scale option.

For **endpoint #3**, the rate of clinical early interventions will be calculated as (number of early interventions)/(total time-person in FAS) and it will be reported together with the 95% Poisson Confidence Interval.

Early interventions include, as defined in CRF (Monitoring Period):

1. Stimulated subject to breathe;
2. Repositioned/opened airway;
3. Held or reduced Respiratory Depressive (RD);
4. Added or increased supplemental oxygen;
5. Ventilation support;
6. Other

**Endpoint #4** will be evaluated reporting a summary of the nurses' satisfaction answers.

To identify the predictive values for EtCO2, RR, SpO2, plethysmography-derived RR, IPI and EWS, which can predict respiratory and other SAE, a sensitivity analysis will be performed (**endpoint #5**), and the following parameters will be reported, for each RC marker:

1. **Sensitivity** = 
$$\frac{(\# \text{ of clinical events "Yes" and with RC marker "Yes"})}{(\# \text{ of clinical events "Yes"})} = \frac{TP}{(TP+FN)}$$
2. **PPV** = 
$$\frac{(\# \text{ of clinical events "Yes" and with RC marker "Yes"})}{(\# \text{ of events with RC marker "Yes"})} = \frac{TP}{(TP+FP)}$$

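### The logistic predictor model covers all, one unnamed or no secondary outcome depending on where one reads, and where it is kept its terms are screened on univariable results that the odds ratios then ignore

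*Protocol*

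**What the plan says.** Three places set out the analysis of the secondary outcomes, and they differ on the logistic model.

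- Protocol synopsis, Statistics: "For all secondary outcomes the logistic regression model will be used to check potential predictors".
- Protocol 12.3: "For one secondary outcome the logistic regression model will be used to check potential predictors". The outcome is not named.
- SAP 7.9.2: no logistic model. Endpoints 1 and 2 get a Chi-square or Fisher test and, if exposure differs between phases, event rates: "The Poisson regression model will be used to calculate the Incidence Rate ratio (IRR), with the d-scale option". Endpoint 3 gets a Poisson rate and endpoint 4 a summary of survey answers. For endpoint 5, on the monitored parameters "which can predict respiratory and other SAE, a sensitivity analysis will be performed", the outputs are sensitivity and positive predictive value.

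Both protocol passages go on to bivariate odds ratios with 95% intervals and then to the building rule: "A multivariate logistic regression model will be performed according to univariate model's results". Neither gives candidate predictors, an entry threshold, a limit on terms, shrinkage or internal validation. Protocol 12.3 sets a two-sided 0.05 level, rules out multiplicity adjustment, and passes the specification on: "Details of endpoints analyses and additional analysis will be described in the Statistical Analysis Plan". In the SAP, the odds ratio survives only in the abbreviation list (Section 2), although its version history says version 1.1 was aligned with protocol version 2.0.

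**The concern.** A multivariable model whose terms are chosen by univariable results uses the same events twice, once to select and once to estimate. The printed intervals assume the terms were fixed in advance. With no adjustment and no stated candidate list, the chance of at least one spurious predictor rises with the number of variables tried, and the reader cannot tell how many were tried.

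The scope conflict adds to this. While the protocol says every outcome in one place and one unnamed outcome in another, and the SAP is silent, both outcome and predictors could be settled after the data are seen. Protocol 9.2 expects the study's information to help design a later outcome study, so over-claimed predictors would carry forward.

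**Working it through.** **1. The plan's sample size.** The SAP plans on "a minimum proportion of 10% of patients with RC markers with a sample size of 182 subjects", with a 95% interval of half-width 5% and probability at least 0.80 of achieving it. For X ~ Binomial(n, 0.10), the probability that the Clopper-Pearson half-width is at most 0.05 first reaches 0.80 at n = 179 and is 0.855 at n = 182, so 182 is reproduced. Inflation: 182 × 1.15 = 209.3, about 210. Protocol 12.1 instead has "a minimum proportion of 10% of patients with RC markers with a sample size of 260 patients"; 260 × 1.15 = 299, which does not lead to 210. I therefore use 182.

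**2. Events available.** Neither document states an event count for any secondary outcome. Events = N × proportion at N = 182:

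| Outcome and source | Proportion | Events |
|---|---|---|
| Any RC marker, planning minimum (SAP 6) | 10% | 18.2 |
| Prolonged desaturation, upper figure (protocol 3.1) | 37% | 67.3 |
| Respiratory failure (protocol 3.1) | 0.2% to 3.4% | 0.4 to 6.2 |

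**3. False selection.** Assumptions, none of them in the documents: 15 independent standard-normal candidates, one real (odds ratio 1.5 per SD) and 14 null, and a screen at p<0.05. If the 14 null tests are independent, P(at least one passes) = 1 − 0.95^14 = 51%. Repeated simulations with n = 182 gave:

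- about 18 events: 49% to 52% of datasets with at least one false predictor passing the screen, and 45% with one still significant in the joint model;
- about 66 to 68 events: 47% to 53% passing the screen.

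The result depends on the number of candidates. With all candidates null, the proportion with a false predictor significant in the joint model was 36% for 10 candidates and 61% for 20 at 18 events, and 37% and 61% at 73 events.

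A five-term prespecified Firth model at about 18 events gave at least one false significant term in 17%. Four null terms would give 1 − 0.95^4 = 19% nominally. The closest like-for-like comparison is thus 45% against 17%.

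**4. Exaggeration.** With true odds ratio 1.5 and 10 candidates, the average odds ratio among significant results was 2.62 at 9 events, 2.01 at 18, 1.88 at 26 and 1.63 at 73. This does depend on events.

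**5. Does the screen cause the exaggeration?** At n = 182 and about 18 events, with true odds ratio 1.5:

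| Strategy | Real predictor kept or significant | Mean odds ratio when so |
|---|---|---|
| 15-candidate screen | 37% to 39% | 2.03 to 2.04 |
| One prespecified predictor, no screen | 35% to 37% | 2.02 to 2.08 |
| Five-term Firth model | 34% to 36% | 1.99 |

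The three are almost the same. Low retention and inflated estimates come from few events and from looking only at significant results, not from the screen.

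**The case against.** The strongest reply is that no screened model would be run. Protocol 12.2 says the SAP holds the detailed analyses, SAP 7.9.2 gives every secondary endpoint another method, and protocol 12.2 requires departures from either document to be described and justified in the final report. The synopsis's wider scope is also probably a slip, since it goes on to analyse other secondary outcomes by sensitivity and specificity. This stands as far as it goes: the harm is conditional on the protocol rule being followed. But the rule is still in the protocol, and the SAP nowhere says that it was dropped. SAP 7.12 settles nothing either way, because it covers possible changes to the per-protocol cut-offs and is not a log of differences from the protocol.

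A reader might infer something stronger: that the trial will have about 18 events and that this scarcity produces the false predictors. The documents do not support that. Eighteen is the planning minimum for the primary endpoint times the SAP's 182, applied to an outcome that the protocol never names; the documents' own proportions allow from under 1 to about 67. False selection was also the same at about 67 events as at 18. Nor does it follow that a prespecified model would cure the inflated odds ratios, as step 5 shows.

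**Conclusion.** The inconsistency between the synopsis, protocol 12.3 and SAP 7.9.2 is certain and needs no assumption. So is the invalidity of intervals that ignore a data-driven choice of terms, if the protocol rule is followed.

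The size is conditional. With 15 independent candidates and a p<0.05 screen, about half of datasets would select at least one false predictor, at any event count examined. For 10 to 20 null candidates, a false predictor reaches joint significance in about 36% to 61%. A five-term prespecified model has about 17%. Exaggeration of significant odds ratios is a separate matter of few events. It would apply if the outcome is RC-marker occurrence near 10% and would be worse for respiratory failure, and removing the screen does not correct it. The change is worth making because it is cheap and the protocol text as it stands permits the problem.

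**What to change.** Delete the univariable screen, and make the synopsis, protocol 12.3 and SAP 7.9.2 say the same thing by one of two routes.

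1. Remove the logistic model from the protocol, as the SAP already has it, and record that it was dropped.
2. Name one outcome and prespecify in the SAP a short penalised logistic model (for example Firth), labelled exploratory, with all terms and intervals reported whatever their significance. Full reporting matters because picking out significant terms brings the exaggeration back.

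Under route 2, if the outcome is RC-marker occurrence, use only the two markers common to both devices (SpO2 and RR) or fit the model within device. Protocol 4.1.1 gives Capnostream four markers and PM1000N-RR two, so a pooled device odds ratio would partly measure the definition. Keep the term count small: five terms on 18 events is 18/5 = 3.6 events per term. Confirm that each chosen predictor is recorded as an analysis variable; the ARISCAT and POSPOM scores, for instance, are not listed as data items in protocol Table 2 or 8.5.

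The cost is wording in three places and no new procedures. The downside is that other candidate predictors are described but not modelled.

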## 13. Ethics

### 13.1 Statement(s) of Compliance

This clinical study will be conducted in compliance with the Declaration of Helsinki (2013), ISO 14155:2011 and local laws and regulations, including data protection laws, the Clinical Trial Agreement, GCP and the CIP. All principles of the Declaration of Helsinki have been implemented in this clinical study by means of the informed consent process, EC approval, clinical study training, clinical trial registration, risk-benefit assessment and publication policy. Adverse Event and Device Deficiency handling in the LIFEGUARD will be ISO 14155:2011 compliant, with the following exception: only those adverse events which are deemed to have an underlying respiratory cause, all Serious AEs, ADEs and DDs will be collected. Medtronic will prepare all the required regulatory authority documents and send them to the respective authority, if applicable.

The clinical study will not begin until EC and regulatory authority approvals, as appropriate, are received.

### 13.2 Ethics Committee

Prior to enrolling patients in this clinical study, each investigation site's EC will be required to approve the current Clinical Investigation Plan, the Patient Information and Informed Consent form, including any other written information to be provided to the patients and, if applicable, materials used to recruit patients. EC approval of the clinical study must be received in the form of a letter and provided to Medtronic before commencement of the clinical study at an investigation site. The approval letter must contain enough information to identify the version or date of the documents approved. If this information is not contained in the approval letter, it must be retrievable from the corresponding submission letter. In addition, the approval letter needs to be accompanied by an EC roster or letter of compliance, to allow verification that the investigator, other investigation site personnel, and/or Medtronic personnel are not members of the EC. If they are members of the EC, written documentation is required stating that he/she did not participate in the approval process. If the EC imposes any additional requirements (e.g. safety reports, progress reports etc.), Medtronic will prepare the required documents and send them to the EC.

EC must inform Medtronic of any change in status of its approval once the investigational site has started enrollment. If any action is taken by an EC with respect to the investigation, that information will be sent directly to Medtronic who will immediately inform the investigator.

### 13.3 Regulatory Requirements / Competent Authorities

The study shall be conducted in accordance with the laws and regulations of the countries in which the clinical study is conducted, including data protection laws. In countries where submission to the regulatory authority is required per local law, no patients will be enrolled in the clinical study until the particular regulatory authority has approved the current Clinical Investigation Plan of the clinical study and other documents as required according to the local requirements. If the regulatory authority imposes any additional requirements (e.g. safety reports, progress reports etc.), Medtronic will prepare the required documents and send them to the respective authority.

### 13.4 Patient Compensation and Indemnification

While a fee will be provided to the participating centers for each enrolled patient, no additional fee/reimbursement will be provided to the patients.

This trial is conducted in Germany, therefore reimbursement and indemnification will be addressed on a country specific basis in the study documents and site Clinical Trial Agreements.

Patients are treated according to general clinical practice, so no extra tests or follow-ups are required and therefore no risks other than the risks typically associated with a routine device use are anticipated. If injuries happen, it will be treated in the same manner as per routine clinical practice. Costs of these treatments will be covered by the national health insurance (as applicable per country) as in usual clinical practice. The patient pays his/her co-payment for that treatment. No special compensation will be paid by the Sponsor.

---

## 14. Study Administration

### 14.1 Monitoring

It is the responsibility of Medtronic to ensure proper monitoring of the study per regulations. Appropriately trained Medtronic personnel or delegates appointed by Medtronic will perform study monitoring at the study center in order to ensure that the study is conducted in accordance with the Clinical Investigation Plan (CIP), the Clinical Trial Agreement, and applicable regulatory requirements. Medtronic must therefore be allowed access to the patient's clinic and hospital records when so requested as per the Patient Consent Form and Clinical Trial Agreement.

Frequency of monitoring visits will occur based on patient enrollment, duration of the study, study compliance, findings from previous monitoring visits and any suspected inconsistency in data that requires investigation. Regulatory documents (e.g., Informed Consent Form, EC approval letters and Clinical Trial Agreements, etc.) will be reviewed at each study center.

A Study Initiation Visit will be conducted after the EC approval and study agreement signature to train the investigational site. Interim Monitoring visits will be conducted to assess site study progress, the investigator's adherence to the CIP, regulatory compliance including but not limited to EC approval and review of the study, maintenance of records and reports, and review of source documents against patient eCRFs. Monitors facilitate site regulatory and study compliance by identifying findings of non-

compliance and communicating those findings along with recommendations for preventative/ corrective actions to site personnel. This may be done in collaboration with the study management and the local field personnel, if available. Communication with the site personnel occurs during the visit and following the visit via a written follow-up letter. Monitors may work with study personnel to determine appropriate corrective action recommendations and to identify trends within the study or at a particular center. Study closure visits will be conducted via telephone or on site at each enrolling study center.

The Principal Investigator should be available during the Monitoring Visits or at least should be available to discuss by phone any eventual finding resulting from the Monitoring Visit.

